7.5.6. Suspected or Confirmed Organ Transplant Rejection

All cases of suspected or confirmed organ transplant rejection must be reported within EDC system as MAAEs. All cases of biopsy-proven organ transplant rejection should be reported as SAEs, based on criteria for a medically important event ([Section 7.5.2](#)). As an SAE, the event should be reported to the Sponsor or designee immediately and, in all circumstances, within 24 hours as per [Section 7.5.12](#) (Reporting SAEs). Suspected cases of organ transplant rejection that meet the criteria for SAEs should also be reported as SAEs per the same processes. For confirmed AND suspected cases of organ transplant rejection, the investigator should provide all relevant data (eg, signs and symptoms, associated laboratory tests, diagnostic testing including imaging and procedures, and biopsy results) to the Sponsor within 24 hours of these data being available.

After Day 57 (for unvaccinated SOT recipients of 2 doses [Group A1]), after Day 113 (unvaccinated SOT recipients of 3 doses [Group A2]), or after Day 29 (previously vaccinated SOT

recipients who receive dose 3 [Group A3]) or after BD-D29 for SOT participants who receive a BD [Group B2, Group B3, and Group B4]), the investigator will review the standard-of-care laboratory assessments and report any suspected or confirmed event of organ transplant rejection until the EOS.

7.5.7. Recording and Follow-up of Pregnancy

Female individuals who have a positive pregnancy test at Screening should not be enrolled; participants who have a positive pregnancy test any time during the study should receive no further dosing with vaccine but should be asked to remain in the study and be monitored for safety.

Details of all pregnancies in female participants will be collected after the start of study treatment and until the end of their participation in the study.

- If a pregnancy is reported, the investigator should inform the Sponsor within 24 hours of learning of the pregnancy and should follow the procedures outlined in this section.
- Abnormal pregnancy outcomes (eg, spontaneous abortion, fetal death, stillbirth, congenital anomalies, ectopic pregnancy) are considered SAEs.

Pregnancies occurring in participants after enrollment must be reported to Sponsor or designee within 24 hours of the study site learning of its occurrence, using the SAE Mailbox, the SAE Hotline, or the SAE Fax line ([Section 7.5.12](#)). If the participant agrees to submit this information, the pregnancy must be followed to determine the outcome, including spontaneous or voluntary termination, details of the birth, and the presence or absence of any birth defects, congenital abnormalities, or maternal and/or newborn complications. This follow-up should occur even if intended duration of the safety follow-up for the study has ended. Pregnancy report forms will be distributed to the study site to be used for this purpose. The investigator must immediately (within 24 hours of awareness) report to the Sponsor any pregnancy resulting in an abnormal outcome according to the procedures described for SAEs.

7.5.8. Eliciting and Documenting Adverse Events

The investigator is responsible for ensuring that all AEs and SAEs are recorded in the eCRF and reported to the Sponsor.

Solicited ARs will be collected from Day 1 through 7 days after each dose. Other (unsolicited) AEs will be collected from Day 1 through 28 days after each dose.

Both MAAEs and SAEs will be collected from participants as specified in the applicable SoE until the end of their participation in the study. Any AEs that occur before administration of vaccine will be analyzed separately from AEs.

At every study site visit or telephone contact, participants will be asked a standard question to elicit any medically related changes in their well-being (including COVID-19 symptoms) according to the scripts provided. Participants will also be asked if they have been hospitalized, had any accidents, used any new medications, changed concomitant medication regimens (both prescription and over-the-counter medications), or had any nonstudy vaccinations.

In addition to participant observations, physical examination findings or data relevant to participant safety classified as an AE will be documented on the AE page of the eCRF.

After the initial AE/SAE report, the investigator is required to proactively follow each participant at subsequent visits/contacts. All AEs and SAEs will be treated as medically appropriate and followed until resolution, stabilization, the event is otherwise explained, or the participant is LTFU (as defined in [Section 6.4](#)).

7.5.9. Assessment of Severity

An event is defined as “serious” when it meets at least one of the predefined outcomes as described in the definition of an SAE ([Section 7.5.2](#)), NOT when it is rated as severe.

The severity of an AR or AE refers to the extent to which it affects the participant’s daily activities. The Toxicity Grading Scale for Healthy Adult and Adolescent Volunteers Enrolled in Preventative Vaccine Clinical Trials ([DHHS 2007](#)) will be used to categorize local and systemic reactogenicity events (solicited ARs), clinical laboratory test results and vital sign measurements observed during this study. Specific criteria for local and systemic reactogenicity events are presented in [Section 7.5.3](#). Specific criteria for vital signs and laboratory abnormalities are presented in [Section 10.4](#), Appendix 4, and will be graded if outside of the reference range for the laboratory utilized. For laboratory abnormalities not included in the protocol-defined grading system, the guidelines for all unsolicited AEs will be used to describe severity.

The determination of severity for all unsolicited AEs should be made by the investigator based upon medical judgment and the definitions of severity as follows:

- Mild: These events do not interfere with the participant’s daily activities.
- Moderate: These events cause some interference with the participant’s daily activities and require limited or no medical intervention.
- Severe: These events prevent the participant’s daily activity and require intensive therapeutic intervention.

Determination of Severe COVID-19 is described in [Section 7.3](#).

Study staff should elicit from the participant the impact of AEs on the participant’s activities of daily living to assess severity and document appropriately in the participant’s source

documentation. Changes in the severity of an AE should be documented in the participant's source documentation to allow an assessment of the duration of the event at each level of severity to be performed. An AE characterized as intermittent requires documentation of onset and duration of each episode. An AE that fluctuates in severity during the course of the event is reported once in the eCRF at the highest severity observed.

7.5.10. Assessment of Causality

The investigator's assessment of an AE's relationship to vaccine is part of the documentation process but is not a factor in determining what is or is not reported in the study.

The investigator will assess causality (ie, whether there is a reasonable possibility that the vaccine caused the event) for all AEs and SAEs. The relationship will be characterized using the following classification:

Not related: There is not a reasonable possibility of a relationship to the vaccine. Participant did not receive the vaccine OR temporal sequence of the AE onset relative to administration of the vaccine is not reasonable OR the AE is more likely explained by another cause than the vaccine.

Related: There is a reasonable possibility of a relationship to the vaccine. There is evidence of exposure to the vaccine. The temporal sequence of the AE onset relative to the administration of the vaccine is reasonable. The AE is more likely explained by the vaccine than by another cause.

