7.5. Safety Definitions and Related Procedures

7.5.1. Adverse Event

An AE is defined as any untoward medical occurrence associated with the use of a drug in humans, whether or not it is considered drug-related.

Events Meeting the Adverse Event Definition

- Exacerbation of a chronic or intermittent pre-existing condition, including an increase in the frequency and/or severity of the condition.
- New conditions detected or diagnosed after the first dose of vaccine even though they may have been present before the start of the study.

Events NOT Meeting the Adverse Event Definition

- Medical or surgical procedure (eg, endoscopy, appendectomy): the condition that leads to the procedure should be the AE.
- Situations in which an untoward medical occurrence did not occur (social and/or convenience admission to a hospital).

An AR is any AE for which there is a reasonable possibility that the vaccine caused the AE ([Section 7.5.10](#)). For the purposes of investigational new drug safety reporting, “reasonable possibility” means that there is evidence to suggest a causal relationship between the vaccine and the AE.

An unsolicited AE is any AE reported by the participant that is not specified as a solicited AR in the protocol or is specified as a solicited AR but starts outside the protocol-defined period for reporting solicited ARs (ie, for the 7 days after each dose of vaccine).

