7.6.2. Internal Safety Committee and Study Pause Rules

An internal safety team (IST) will be created specifically to review safety and reactogenicity data after:

- At least 10 SOT recipients have received their third dose of study vaccine and have at least 7 days of reactogenicity data
- At least 55 SOT recipients have received their third dose of study vaccine, unless a safety event requires earlier review
- Any other ad hoc safety concerns based on ongoing safety surveillance

The IST will operate under the rules of an approved charter that will be written and reviewed at the organizational meeting of the IST. Details regarding the IST composition, responsibilities, procedures, and frequency of data review will be defined in its charter.

Study pause rules will be implemented and will only remain in effect until all study participants who consented to receive a third dose have received their third dose of vaccine. If the following occur, vaccination with third dose may be temporarily suspended until expedited Sponsor review of safety data take place to assess over all potential safety risk to SOT recipients:

- Reactogenicity: Two Grade 4 solicited local or systemic reactogenicities that are related to the vaccine
- Hypersensitivity: Five SOT recipients experiencing a severe systemic allergic reaction that is related to the vaccine
- Adverse Event: Three SAEs or Grade 4 AEs (laboratory and vital sign abnormalities per [Section 10.4](#), Appendix 4 reported as AEs by the investigator) that are related to the vaccine
- Fatal Outcome: One death that is related to the vaccine

The investigators, study medical monitor, and Sponsor will monitor for events that could trigger a study pause. The investigator or designee is responsible for reporting to the Sponsor, via the EDC system within 24 hours of observation, each event potentially meeting any pause rule criterion.

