8.1. Sample Size

The study vaccine, mRNA-1273, is currently being evaluated in a pivotal Phase 3 efficacy, safety, and immunogenicity study in an adult population at high risk of COVID-19 disease (Study P301). Success criteria for early efficacy was met at the first interim analysis based on 95 adjudicated cases with a vaccine efficacy of 94.5% (95% CI: 86.5%, 97.8%; one-sided p value < 0.0001 of testing the null hypothesis of $VE \leq 30\%$). Study P301 is expected to provide immunogenicity data by which an Ab threshold of protection against COVID-19 will be estimated.

This current study, which aims to evaluate Ab responses following a second, third, or fourth (booster) dose of mRNA-1273 vaccine among kidney and liver transplant recipients, is expected to provide clinical data to determine whether vaccination with mRNA-1273 will induce vaccine response in this cohort of immunocompromised participants that is comparable to those of the participants in Study P301 and comparable to those of the concurrently assessed cohort of participants in this study with normal immune function.

With 200 SOT participants, if the true AE rate of biopsy-proven organ rejection is 3%, there is approximately >95% probability to observe at least 1 subject reporting such an AE.

The planned sample size of approximately 240 participants (220 unvaccinated or previously vaccinated participants who have had a kidney or liver transplant and 20 unvaccinated healthy participants) who receive 2-dose regimen and 3-dose regimens of 100 µg of mRNA-1273, or 100 µg BD regimen are expected to provide useful estimates of Ab response at Day 29 for previously vaccinated SOT recipients who receive dose 3 in Part A, and Day 113 for unvaccinated SOT recipients who receive the 3-dose regimen, at Day 57 for unvaccinated participants who receive the 2-dose regimen, and at BD-D29 for Part B participants (participants who receive a BD) (primary endpoints), respectively, for comparison to results from Study P301 (if available at the time of database lock). The healthy adult participants will be used primarily as a biological control for the CMI analysis. This study is designed for estimation purposes, and no between-group comparisons are planned.

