#### **6.3.1.2.TEAEs by System Organ Class and Preferred Term**

The following summary tables of TEAEs will be provided by SOC and PT using frequency counts and percentages (i.e., number and percentage of subjects with an event):

- All unsolicited TEAEs
- All unsolicited TEAEs by the subgroups named in [Section 6.1](#)
- All unsolicited TEAEs that are treatment-related
- All serious TEAEs
- All serious TEAEs that are treatment-related
- All unsolicited TEAEs leading to discontinuation from study vaccine
- All unsolicited TEAEs leading to discontinuation from participation in the study

Confidential

- All unsolicited Severe TEAEs
- All unsolicited Severe TEAEs that are treatment-related
- All unsolicited medically-attended TEAEs
- All unsolicited medically-attended TEAEs that are treatment-related
- All TEAEs adjudicated as biopsy-proven organ rejection
- All TEAEs that are AESI

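### Protocol Section 7.5.10 asks about a reasonable possibility of causation but then classifies by which cause is more likely, so the count of related events depends on which standard a site applies

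*Protocol*

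**What the plan says.** **The question put to the investigator.** Protocol Section 7.5.10 states: "The investigator will assess causality (ie, whether there is a reasonable possibility that the vaccine caused the event) for all AEs and SAEs". Both of its categories open with the same reasonable-possibility phrase, and Section 7.5.12 uses it again for SAEs. Section 7.5.1 builds the definition of an adverse reaction on it: "An AR is any AE for which there is a reasonable possibility that the vaccine caused the AE". For investigational new drug safety reporting, Section 7.5.1 adds that the phrase "means that there is evidence to suggest a causal relationship between the vaccine and the AE".

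**The rule for answering it.** The *Related* category in Section 7.5.10 also requires exposure and reasonable timing, and ends: "The AE is more likely explained by the vaccine than by another cause". The *Not related* category lists alternatives, the last being "OR the AE is more likely explained by another cause than the vaccine". The OR makes that alternative sufficient by itself.

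**Where the label is used.**
- Section 7.6.2: all four third-dose pause criteria count related events, for example "Fatal Outcome: One death that is related to the vaccine".
- Section 6.2: one ground for withholding further injection is an unsolicited AE that is both severe and considered related.
- Protocol Table 6 and SAP Sections 6.3.1.1, 6.3.1.2 and 6.3.1.4: treatment-related summaries, such as "All serious TEAEs that are treatment-related".

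**The concern.** One section contains two standards. The first asks whether vaccine causation is reasonably possible; the second asks whether it is the likelier explanation. They disagree for every event whose chance of vaccine causation is real but not above one half. In transplant recipients such events should be common, because there is usually a competing explanation.

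Two sites could code the same event differently and both be following Section 7.5.10. Where the stricter clause is used, related events are undercounted in the related-AE, related-SAE and related severe-AE tables, and in the pause and withholding rules that use the same word. The study has no concurrent unvaccinated transplant control (Protocol Section 8.3.2), so readers are likely to give the related columns some weight.

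**Working it through.** **Step 1. The two standards side by side** (exposure and timing taken as satisfied).

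| Chance that the vaccine caused the event | Reasonable-possibility standard | Closing clauses of 7.5.10 |
|---|---|---|
| No reasonable possibility | Not related | Not related |
| Real, but below 50% | Related | Not related |
| Exactly 50% | Related | Neither clause met |
| Above 50% | Related | Related |

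The second row is the contradiction. The third is a gap.

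**Step 2. The plan's own rejection figure.** Protocol Section 8.1 says: "With 200 SOT participants, if the true AE rate of biopsy-proven organ rejection is 3%, there is approximately >95% probability to observe at least 1" participant reporting it. Check: 1 − 0.97^200 = 0.9977, consistent with the stated figure. This 3% is a sizing assumption; the documents give no background rejection rate.

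**Step 3. What a more-likely-than-not test implies, on rate alone.** Let RR be the rate with vaccine divided by the rate without. RR is an assumption; the documents give none. If the excess is spread evenly over the period and nothing else is known about the case, the chance that a given case is vaccine-caused is (RR − 1)/RR:

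| RR | 1.25 | 1.5 | 1.75 | 1.9 | 2.0 | 2.1 | 3.0 |
|---|---|---|---|---|---|---|---|
| Chance | 20.0% | 33.3% | 42.9% | 47.4% | 50.0% | 52.4% | 66.7% |

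Setting (RR − 1)/RR = 1/2 gives RR = 2.

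**Step 4. Illustrative counts, n = 200, RR = 1.9.**
- If 3% is the rate without vaccine: 200 × 0.03 × 1.9 = 11.4 rejections, of which 200 × 0.03 × 0.9 = 5.4 are vaccine-caused.
- If 3% is the total rate on vaccine: 200 × 0.03 = 6 rejections, of which 6 × 0.474 = 2.8 are vaccine-caused.
- For rates without vaccine of 1% to 5%, the vaccine-caused count runs from 200 × 0.01 × 0.9 = 1.8 to 200 × 0.05 × 0.9 = 9.0.

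**Step 5. How fragile the RR = 2 threshold is.**
- *Another cause read singly.* If the vaccine is weighed against each rival separately and background is split evenly over k causes, the condition is RR − 1 > 1/k. The threshold falls to 1.5 for k = 2 and 1.33 for k = 3.
- *Clustering after dosing.* If a 1.9-fold average over 365 days came entirely from one 28-day window, RR inside it would be 1 + 0.9 × 365/28 = 12.7 and the chance 11.7/12.7 = 92%. Those cases would pass the stricter test.

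**Step 6. The opposite risk.** With a 3% rate, n = 200 and no vaccine effect, the binomial probability of three or more rejections is 0.94. If every rejection were labelled related, three related SAEs would be likely from background alone. The 200 overstates the exposed group, because the Section 7.6.2 rules concern third-dose vaccination only.

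**The case against.** **A reader might infer that vaccine-triggered rejection would be classed unrelated, and so missed, even if the vaccine nearly doubled its rate. The documents do not support that.** Biopsy-proven rejection is a primary endpoint with no causality filter. Every biopsy-proven case is to be reported as an SAE (Section 7.5.6). Biopsy-proven cases, and suspected cases meeting the stated criteria, go to the independent Safety Review Committee, after which the sponsor may suspend enrolment or dosing (Section 7.6.1). Adjudicated rejections are summarised whatever their relatedness (SAP Sections 6.3.1 to 6.3.1.2). Section 7.5.10 itself says causality does not decide what is reported.

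**The RR = 2 figure is a population fraction, not a verdict on a case.** Investigators weigh timing, laboratory results and biopsy findings, so probabilities differ between cases even when the average is 47%. This stands; the figure can serve only as an illustration.

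**Section 7.5.1 is not plainly a rival standard.** Its gloss is limited to investigational new drug reporting, and its adverse-reaction definition cross-refers to 7.5.10. That is fair. But the opening question of 7.5.10, the heads of both its categories and Section 7.5.12 carry no such limit, so the conflict remains inside 7.5.10.

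**The reach into the pause rules is limited.** They concern the third dose, lapse once consenting participants have received it, and say vaccination may be suspended. Solicited reactions are all treated as causally related (Section 7.5.3), so the reactogenicity trigger is unaffected. The internal safety team can also review ad hoc concerns. All of this stands, but the remaining triggers, the withholding ground and the related tables still use the disputed label. Committee review of rejection does not cover other related SAEs, severe AEs or deaths.

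**Conclusion.** The point holds as a contradiction in a stated classification rule. Section 7.5.10 gives two incompatible standards for one label, with an unassigned case at an even chance. The direction is clear: the stricter reading can only lower the number of related events. The size cannot be derived from the documents, which give no background rate and no relative rate. The RR = 2 threshold rests on three assumptions: judgment on rate alone, all other causes taken together, and an evenly spread excess. Relaxing the second or third lowers it, and case-level evidence can carry an individual case past the test at a lower relative rate. Capture of rejection is not in question. What is affected is the meaning of the treatment-related tables and of the related-event counts in Sections 7.6.2 and 6.2.

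**What to change.** Reconcile the two more-likely-explained clauses in Section 7.5.10 with that section's opening question and with Sections 7.5.1 and 7.5.12. One causality standard should then apply, and *Related* and *Not related* should be complementary and exhaustive. Issue a site memo. Because the label bears on pausing and withholding, the sponsor should decide the standard and confirm that the rules in Sections 7.6.2 and 6.2 are read with the same definition as the treatment-related tables. No pause threshold needs to be rewritten for this.

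The drafting cost is a short wording change and the memo. There is a substantive cost if the reasonable-possibility wording is the one kept: more events, including some background events, will be labelled related. Related-event figures would then look less favourable, and the related-SAE count could be reached more readily, as Step 6 shows in its extreme form. The sponsor should weigh that openly when reconciling the text.

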7.5.11. Reporting Adverse Events

The investigator is responsible for reporting all AEs that are observed or reported during the study, regardless of their relationship to vaccine or their clinical significance. If there is any doubt as to whether a clinical observation is an AE, the event should be reported.

All unsolicited AEs reported or observed during the study will be recorded on the AE page of the eCRF. Information to be collected includes the type of event, time of onset, investigator specified assessment of severity (impact on activities of daily living) and relationship to vaccine, time of resolution of the event, seriousness, as well as any required treatment or evaluations, and outcome. The unsolicited AEs resulting from concurrent illnesses, reactions to concurrent illnesses, reactions to concurrent medications, or progression of disease states must also be reported. All AEs will be followed until they are resolved or stable or judged by the investigator to be not clinically significant. The Medical Dictionary for Regulatory Activities (MedDRA) will be used to code all unsolicited AEs.

Any medical condition that is present at the time that the participant is screened but does not deteriorate should not be reported as an unsolicited AE. However, if it deteriorates at any time during the study, it should be recorded as an unsolicited AE.

